8.9. Data Monitoring Committee

An external data monitoring committee (DMC) comprised of an independent statistician and two independent gastroenterologists will review the progress of the study and perform interim reviews of safety data and provide recommendation to Gilead whether the nature, frequency, and severity of adverse effects associated with study treatment warrant the early termination of the study in the best interests of the participants, whether the study should continue as planned, or the study should continue with modifications.

The DMC will meet twice to evaluate all available safety data of the study. The initial meeting will occur after approximately 20% of the planned total number of subjects complete their Week 10 visit. Following this, the next meeting will occur after approximately 50% of the subjects reach Week 10. Additionally, the DMC members may request an unscheduled review of the study data based on a concern for subject safety. An ad hoc DMC meeting may be triggered by the following conditions:

- ≥ 2 subjects develop the same (by PT) related, Grade 4, unexpected AE in the infections and infestations SOC
- ≥ 2 subjects develop any related, Grade 4, thromboembolic events that have been positively adjudicated by the adjudication committee (see Section 8.10)
- Any subject develops a Grade 5, related, unexpected AE. The definition of an unexpected AE will be based on the reference safety information that is on file at the time the event occurs

After a minimum of 35 subjects (estimated to be 7 from placebo group and 14 from each filgotinib treatment group based on randomization ratio) are enrolled and complete Week 10 visit or discontinue from the study, an interim futility analysis will be conducted to evaluate efficacy improvement in fistulizing disease. The cumulative safety analysis and summary statistics to evaluate perianal fistula closure of external openings, and CCI [REDACTED]

[REDACTED] improvement will be generated and provided to the DMC. The DMC will make a recommendation to either continue the study without modification or recommend that the study be halted due to lack of efficacy, and will be based on the totality of data available at the time of the interim analysis.

The DMC's specific activities will be defined by a mutually agreed upon charter, which will define the DMC's membership, conduct and meeting schedule.

While the DMC will be asked to advise Gilead regarding future conduct of the study, including possible early study termination, Gilead retains final decision-making authority on all aspects of the study. If the DMC recommends stopping the study for lack of efficacy, a Gilead executive team will be unblinded to confirm the DMC recommendation.

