Administration of filgotinib produces an increase in embryofetal malformations in pregnant rats and rabbits at exposures similar to, or slightly higher than, exposures associated with a 200 mg once daily dose in CD subjects; this risk will be mitigated with the use of highly effective contraception for subjects of child-bearing potential.

JAK inhibition is expected to increase the risk of infection based on mechanism of action. Across global studies with filgotinib, in general, active treatment arms have increased incidences of infection versus placebo. In the present protocol, treatment interruption and discontinuation considerations surrounding infections are incorporated and sites and investigators will be trained regarding such circumstances. All subjects will be screened for tuberculosis (TB) and subjects with active infections will be excluded. Malignancy has been reported in subjects on filgotinib; in the present trial, subjects will be required to have up to date colorectal cancer screening and surveillance and subjects with recent malignancies will be excluded as outlined in the eligibility criteria. For further details about infections and malignancies, please reference the IB.

The potential benefits of JAK inhibition include improvement in clinical symptoms and mucosal and endoscopic healing. JAK inhibition may be efficacious in the treatment of IBD based on results from FITZROY. A lack of response contingency after Week 10 will enable early access to active drug when clinically indicated. In FITZROY, an increase in mean hemoglobin concentration was observed, without difference between filgotinib and placebo. No clinically significant changes from baseline in mean neutrophil counts or liver function tests were observed at 10 weeks. Filgotinib treated subjects showed an increase in HDL and no significant change in LDL. Lipid and hemoglobin effects represent potential benefits in this population.

An independent data monitoring committee (DMC) appointed to monitor the study will provide an additional level of risk mitigation. The DMC may advise to continue the study unchanged, to modify the study, or to discontinue the study. The initial meeting will occur after approximately 20% of the planned total number of subjects reach the Week 10 visit. Following this, the next meeting will occur after approximately 50% of subjects reach the Week 10 visit. Additional DMC meetings may be convened, if needed.

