8.10. Cardiovascular Safety Endpoint Adjudication Committee (CVEAC)

An independent adjudication committee will be formed to periodically review and adjudicate all potential major adverse cardiovascular events (MACE) and thromboembolic events in a blinded manner.

The CVEAC's specific activities will be governed by a mutually agreed charter, which will define the CVEAC's membership, conduct, and meeting schedule.

The following events will be adjudicated and classified by the CVEAC:

- Cardiovascular death
- Myocardial infarction
- Stroke
- Arterial thromboembolism
- Venous thromboembolism (eg, deep venous thrombosis, pulmonary embolism)

Further details will be specified in the CVEAC charter.

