#### **2.1.1. Safety Analyses**

An external multidisciplinary DMC will review the progress of the study and perform interim reviews of the safety data in order to protect subject welfare and preserve study integrity. To ensure the best interests of the participants, the DMC will recommend to the sponsor if the nature, frequency, and severity of adverse effects associated with the study treatment warrant the early termination of the study, the continuation of the study, or the continuation of the study with modifications.

The DMC will meet twice to evaluate all available safety data of the study. The initial meeting will occur after approximately 20% of the planned total number of subjects complete their Week 10 visit. Following this, the next meeting will occur after approximately 50% of the subjects reach Week 10. Additionally, the DMC members may request an unscheduled review of the study data based on a concern for subject safety. Additional meetings may be triggered by safety findings, predetermined or otherwise.

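### The predefined ad hoc DMC triggers in Protocol 8.9 leave gaps for severe infections and thromboembolic events; review of those cases rests on scheduled meetings or discretion

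*Protocol*

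**What the plan says.** Protocol 8.9 gives three conditions under which an ad hoc DMC meeting may be called:

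1. At least two "subjects develop the same (by PT) related, Grade 4, unexpected AE in the infections and infestations SOC".
2. At least two "subjects develop any related, Grade 4, thromboembolic events that have been positively adjudicated by the adjudication committee".
3. "Any subject develops a Grade 5, related, unexpected AE", in any system organ class (SOC).

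On expectedness, 8.9 states: "The definition of an unexpected AE will be based on the reference safety information that is on file at the time the event occurs". Protocol 7.4 has the sponsor judge expectedness of SAEs from the reference safety information in the investigator's brochure or the local label.

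Table 7-1 in Protocol 7.2.2 makes Grade 4 (life-threatening) and Grade 5 (death) separate grades. None of the conditions says Grade 4 or higher.

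On adjudication, Protocol 8.10 says: "An independent adjudication committee will be formed to periodically review and adjudicate" potential major cardiovascular and thromboembolic events. The details are left to a charter.

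Two safety meetings are scheduled, the first when about 20% of planned subjects complete Week 10. For the second, SAP 2.1.1 says "the next meeting will occur after approximately 50% of the subjects reach Week 10". A futility look at a minimum of 35 subjects also brings the DMC a cumulative safety analysis.

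On the underlying risk, Protocol 1.5 says: "JAK inhibition is expected to increase the risk of infection based on mechanism of action". It adds that active arms have in general shown more infection than placebo, and it cites the DMC as a further layer of risk mitigation.

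**The concern.** A predefined trigger exists so that review of a serious pattern does not depend on someone choosing to ask for it. Three features of the wording work against that.

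- **Exact grade.** A fatal event does not count towards either pair. It triggers a meeting alone only if it is unexpected. An RSI-expected death can therefore count for less than a Grade 4 event.
- **Same PT and unexpectedness for infections.** Two life-threatening infections coded to different PTs do not pair. Infections already listed in the RSI do not count at all. Expectedness is a reporting concept and does not show whether the arms are out of balance.
- **Prior adjudication for thromboembolism.** The condition is not met until a second committee has ruled.

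At stake is how reliably severe infections and thromboembolic events reach independent unblinded review, above all after the last scheduled safety meeting.

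**Working it through.** **Step 1. Test cases against the listed conditions, read literally.** All events are taken as related.

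| Case | Infection pair | Thromboembolic pair | Single Grade 5 | Any met? |
|---|---|---|---|---|
| Two Grade 4 infections, different PTs, both unexpected | No: PTs differ | n/a | No | None |
| Two Grade 4 infections, same PT, RSI-expected | No: expected | n/a | No | None |
| One fatal infection, RSI-expected | No: Grade 5, expected | n/a | No: expected | None |
| One adjudicated Grade 4 and one fatal RSI-expected thromboembolic event | n/a | No: one Grade 4 only | No: expected | None |
| Two Grade 4 thromboembolic events, not yet adjudicated | n/a | Not until adjudicated | No | None yet |
| One fatal infection, not RSI-expected | No | n/a | Yes | Met by one subject |

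The different-PT and pending-adjudication gaps do not depend on the RSI. The other gaps do.

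**Step 2. Where the scheduled meetings fall.** Planned N is 75, allocated 30/30/15 (Protocol 8.8). The meetings come at 0.20 × 75 = 15 and 0.50 × 75 = 37.5, or about 38 subjects at Week 10. About 75 − 38 = 37 subjects have not reached Week 10 at the last one. The futility look, at 35 or more subjects who have completed Week 10 or discontinued, comes at about the same time. No scheduled safety meeting follows.

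**Step 3. What the same-PT condition costs.** The documents give no Grade 4 infection rate, so the rates and PT counts here are assumptions. Take n = 60 filgotinib subjects (30 + 30). Let p be the chance that a subject has one related Grade 4 infection, spread equally over K PTs, with every event unexpected.

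- At least two subjects, any PT: 1 − (1 − p)^60 − 60p(1 − p)^59.
- At least two sharing a PT: 1 − Σ over m = 0 to K of C(60, m) p^m (1 − p)^(60 − m) × K! / [(K − m)! K^m].

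For p = 5%, the first formula gives 1 − 0.0461 − 0.1455 = 0.808. The full set is:

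| p | ≥2 subjects, any PT | Same PT, K = 3 | Same PT, K = 5 | Same PT, K = 10 |
|---|---|---|---|---|
| 1% | 0.121 | 0.051 | 0.032 | 0.017 |
| 2% | 0.338 | 0.173 | 0.116 | 0.064 |
| 5% | 0.808 | 0.607 | 0.480 | 0.313 |

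For a given K, equally likely PTs make sharing least likely, so unequal frequencies would raise the same-PT figures. If the PTs concerned are RSI-expected, the infection condition cannot be met at any rate.

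**The case against.** The strongest reply is that the listed conditions are not the whole of the oversight. Four parts of it stand and limit the point.

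- **Other routes to a meeting.** A reader might infer that the three conditions are the only event-driven way back to the DMC. They are not. The list in 8.9 is permissive and is not said to be exhaustive. Members may request an unscheduled review on any safety concern. Protocol 1.5 allows further meetings if needed, and SAP 2.1.1 allows them on safety findings whether or not set in advance.
- **Unblinded review outside the DMC.** A reader might infer that an imbalance late in the trial could go without any unblinded review. Protocol 5.1.2 lets sponsor pharmacovigilance staff responsible for signal detection see unblinded cases and group summaries. That is sponsor rather than independent review, but it is review.
- **Two meanings of expected.** Section 1.5 makes a statement about mechanism. Section 8.9 ties expectedness to the RSI, which is not in the documents. It cannot be inferred that severe or fatal infections are RSI-expected.
- **Charters not seen.** Both committees' schedules and conduct sit in charters. It does not follow from the visible text that adjudication is slow or that the DMC sees no data between meetings.

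The permanent discontinuation rules in Protocol 3.5.2 for serious infections and thromboembolic events also protect individual subjects, though they do not replace aggregate review. At a 1% rate even an any-PT rule would be met only about 12% of the time.

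The reply does not close the gap. The further routes to the DMC are discretionary, and the visible text obliges no one to use them for the cases in Step 1.

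**Conclusion.** The point holds as a gap in the predefined triggers, not as an absence of oversight. Four kinds of event meet no listed condition:

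- related Grade 4 infections with differing PTs;
- related Grade 4 or 5 infections that the RSI lists as expected;
- a Grade 4 plus an RSI-expected fatal thromboembolic event;
- Grade 4 thromboembolic events not yet adjudicated.

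It would go too far to say that fatal infections escape the triggers altogether, because one related, unexpected Grade 5 event is enough.

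The size depends on assumed rates. With 10 equally likely PTs, the same-PT condition cuts the chance of meeting the infection trigger from about 0.34 to 0.06 at a 2% rate, and from about 0.81 to 0.31 at 5%. With fewer PTs the loss is smaller. The RSI-dependent gaps may be empty or wide, and the charter may already close some of them. This is a low-cost improvement worth making in a descriptive 75-subject trial.

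**What to change.** Reword the ad hoc conditions in Protocol 8.9, and the DMC charter to match, as follows:

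- **(a) Infections:** at least two subjects with related AEs of Grade 4 or higher in the Infections and Infestations SOC, any PT, regardless of expectedness.
- **(b) Thromboembolism:** at least two subjects with related thromboembolic events of Grade 4 or higher as reported by the investigator. Adjudication runs in parallel and its result is forwarded when available.
- **(c) Deaths:** any related Grade 5 AE, regardless of expectedness.

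SAP 2.1.1 already allows meetings on predetermined findings, so it needs no change of substance. SAP 7.1.7 already plans infection and serious-infection summaries across the whole SOC, so existing tables can serve. The cost is possibly one or two extra DMC calls. No new data collection or subject-level rule is involved.

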8.10. Cardiovascular Safety Endpoint Adjudication Committee (CVEAC)

An independent adjudication committee will be formed to periodically review and adjudicate all potential major adverse cardiovascular events (MACE) and thromboembolic events in a blinded manner.

The CVEAC's specific activities will be governed by a mutually agreed charter, which will define the CVEAC's membership, conduct, and meeting schedule.

The following events will be adjudicated and classified by the CVEAC:

- Cardiovascular death
- Myocardial infarction
- Stroke
- Arterial thromboembolism
- Venous thromboembolism (eg, deep venous thrombosis, pulmonary embolism)

Further details will be specified in the CVEAC charter.

9. RESPONSIBILITIES

9.1. Investigator Responsibilities

9.1.1. Good Clinical Practice

The investigator will ensure that this study is conducted in accordance with the principles of the Declaration of Helsinki, International Council for Harmonisation (ICH) guidelines, or with the laws and regulations of the country in which the research is conducted, whichever affords the greater protection to the study subject. These standards are consistent with the European Union Clinical Trials Directive 2001/20/EC and Good Clinical Practice Directive 2005/28/EC.

The investigator will ensure adherence to the basic principles of Good Clinical Practice, as outlined in 21 CFR 312, subpart D, "Responsibilities of Sponsors and Investigators," 21 CFR, part 50, and 21 CFR, part 56.

The investigator and all applicable subinvestigators will comply with 21 CFR, Part 54, providing documentation of their financial interest or arrangements with Gilead, or proprietary interests in the investigational drug under study. This documentation must be provided prior to the investigator's (and any subinvestigator's) participation in the study. The investigator and subinvestigator agree to notify Gilead of any change in reportable interests during the study and for 1 year following completion of the study. Study completion is defined as the date when the last subject completes the protocol-defined activities.

9.1.2. Institutional Review Board (IRB)/Independent Ethics Committee (IEC) Review and Approval

The investigator (or sponsor as appropriate according to local regulations) will submit this protocol, ICF, and any accompanying material to be provided to the subject (such as advertisements, subject information sheets, or descriptions of the study used to obtain informed consent) to an IRB/IEC. The investigator will not begin any study subject activities until approval from the IRB/IEC has been documented and provided as a letter to the investigator.

Before implementation, the investigator will submit to and receive documented approval from the IRB/IEC any modifications made to the protocol or any accompanying material to be provided to the subject after initial IRB/IEC approval, with the exception of those necessary to reduce immediate risk to study subjects.

9.1.3. Informed Consent

The investigator is responsible for obtaining written informed consent from each individual participating in this study after adequate explanation of the aims, methods, objectives, and potential hazards of the study and before undertaking any study-related procedures. **The study investigator must ensure that the potential risk of infertility is discussed with all male subjects during the informed consent process.** The investigator must use the most current

IRB/IEC approved consent form for documenting written informed consent. Each informed consent (or assent as applicable) will be appropriately signed and dated by the subject or the subject's legally authorized representative and the person conducting the consent discussion, and also by an impartial witness if required by IRB/IEC or local requirements. The consent form will inform subjects about genomic testing and sample retention.

9.1.4. Confidentiality

The investigator must assure that subjects' anonymity will be strictly maintained and that their identities are protected from unauthorized parties. Only subject initials, date of birth, another unique identifier (as allowed by local law) and an identification code will be recorded on any form or biological sample submitted to the Sponsor, IRB/IEC, or laboratory. Laboratory specimens must be labeled in such a way as to protect subject identity while allowing the results to be recorded to the proper subject. Refer to specific laboratory instructions or in accordance with local regulations. NOTE: The investigator must keep a screening log showing codes and names for all subjects screened and for all subjects enrolled in the trial. Subject data will be processed in accordance with all applicable regulations.

The investigator agrees that all information received from Gilead, including but not limited to the IB, this protocol, eCRF, the IMP, and any other study information, remain the sole and exclusive property of Gilead during the conduct of the study and thereafter. This information is not to be disclosed to any third party (except employees or agents directly involved in the conduct of the study or as required by law) without prior written consent from Gilead. The investigator further agrees to take all reasonable precautions to prevent the disclosure by any employee or agent of the study site to any third party or otherwise into the public domain.

9.1.5. Study Files and Retention of Records

The investigator must maintain adequate and accurate records to enable the conduct of the study to be fully documented and the study data to be subsequently verified. These documents should be classified into at least the following two categories: (1) investigator's study file, and (2) subject clinical source documents.

The investigator's study file will contain the protocol/amendments, CRF and query forms, IRB/IEC and governmental approval with correspondence, informed consent, drug records, staff curriculum vitae and authorization forms, and other appropriate documents and correspondence.

The required source data should include sequential notes containing at least the following information for each subject:

- Subject identification (name, date of birth, gender);
- Documentation that subject meets eligibility criteria, ie, history, PE, and confirmation of diagnosis (to support inclusion and exclusion criteria);

- Documentation of the reason(s) a consented subject is not enrolled
- Participation in study (including study number);
- Study discussed and date of informed consent;
- Dates of all visits;
- Documentation that protocol specific procedures were performed;
- Results of efficacy parameters, as required by the protocol;
- Start and end date (including dose regimen) of IMP, including dates of dispensing and return;
- Record of all AEs and other safety parameters (start and end date, and including causality and severity);
- Concomitant medication (including start and end date, dose if relevant; dose changes);
- Date of study completion and reason for early discontinuation, if it occurs.

All clinical study documents must be retained by the investigator until at least 2 years or according to local laws, whichever is longer, after the last approval of a marketing application in an ICH region (ie, US, Europe, or Japan) and until there are no pending or planned marketing applications in an ICH region; or, if no application is filed or if the application is not approved for such indication, until 2 years after the investigation is discontinued and regulatory authorities have been notified. Investigators may be required to retain documents longer if specified by regulatory requirements, by local regulations, or by an agreement with Gilead. The investigator must notify Gilead before destroying any clinical study records.

Should the investigator wish to assign the study records to another party or move them to another location, Gilead must be notified in advance.

If the investigator cannot provide for this archiving requirement at the study site for any or all of the documents, special arrangements must be made between the investigator and Gilead to store these records securely away from the site so that they can be returned sealed to the investigator in case of an inspection. When source documents are required for the continued care of the subject, appropriate copies should be made for storage away from the site.

